#### **For Patients with Measurable Disease (i.e., Target Disease)**

Target Lesions	Non-Target Lesions	New Lesions	Overall Response	Best Overall Response when Confirmation is Required*
CR	CR	No	CR	$\geq 4$ wks. Confirmation**
CR	Non-CR/Non-PD	No	PR	$\geq 4$ wks. Confirmation**
CR	Not evaluated	No	PR	
PR	Non-CR/Non-PD/not evaluated	No	PR	
SD	Non-CR/Non-PD/not evaluated	No	SD	Documented at least once $\geq 4$ wks. from baseline**
PD	Any	Yes or No	PD	no prior SD, PR or CR

Any	PD***	Yes or No	PD	
Any	Any	Yes	PD	

* See RECIST 1.1 manuscript for further details on what is evidence of a new lesion.
 
** Only for non-randomized trials with response as primary endpoint.
 
*** In exceptional circumstances, unequivocal progression in non-target lesions may be accepted as disease progression.
 
Note: Patients with a global deterioration of health status requiring discontinuation of treatment without objective evidence of disease progression at that time should be reported as “symptomatic deterioration.” Every effort should be made to document the objective progression even after discontinuation of treatment.
				

### 6.3.5 DURATION OF RESPONSE

Duration of overall response: The duration of overall response is measured from the time measurement criteria are met for CR or PR (whichever is first recorded) until the first date that recurrent or progressive disease is objectively documented (taking as reference for progressive disease the smallest measurements recorded since the treatment started).

The duration of overall CR is measured from the time measurement criteria are first met for CR until the first date that progressive disease is objectively documented.

Duration of stable disease: Stable disease is measured from the start of the treatment until the criteria for progression are met, taking as reference the smallest measurements recorded since the treatment started, including the baseline measurements.

### 6.3.6 PROGRESSION-FREE SURVIVAL

Progression-free survival (PFS) is defined as the duration of time from start of treatment to time of progression or death, whichever occurs first.

## 6.4 TOXICITY CRITERIA

The following adverse event management guidelines are intended to ensure the safety of each patient while on the study. The descriptions and grading scales found in the revised NCI Common Terminology Criteria for Adverse Events (CTCAE) version 4.0 will be utilized for AE reporting. All appropriate treatment areas should have access to a copy of the CTCAE version 4.0. A copy of the CTCAE version 4.0 can be downloaded from the CTEP web site ([http://ctep.cancer.gov/protocolDevelopment/electronic\\_applications/ctc.htm#ctc\\_40](http://ctep.cancer.gov/protocolDevelopment/electronic_applications/ctc.htm#ctc_40)).

## 7 SAFETY REPORTING REQUIREMENTS/DATA AND SAFETY MONITORING PLAN

### 7.1 DEFINITIONS

#### 7.1.1 ADVERSE EVENT

An adverse event is defined as any reaction, side effect, or untoward event that occurs during the course of the clinical trial associated with the use of a drug in humans, whether or not the event is considered related to the treatment or clinically significant.

•

#### 7.1.2 SUSPECTED ADVERSE REACTION

Suspected adverse reaction means any adverse event for which there is a reasonable possibility that the drug caused the adverse event. For the purposes of IND safety reporting, ‘reasonable possibility’ means there is evidence to suggest a causal relationship between the drug and the adverse event. A suspected adverse reaction implies a lesser degree of certainty about causality than adverse reaction, which means any adverse event caused by a drug.

#### 7.1.3 UNEXPECTED ADVERSE REACTION

An adverse event or suspected adverse reaction is considered “unexpected” if it is not listed in the investigator brochure, package insert, or is not listed at the specificity or severity that has been observed; or, if an investigator brochure is not required or available, is not consistent with the risk information described in the general investigational plan or elsewhere in the current application. “Unexpected”, also refers to adverse events or suspected adverse reactions that are mentioned in the investigator brochure or package insert as occurring with a class of drugs or as anticipated from the pharmacological properties of the drug, but are not specifically mentioned as occurring with the particular drug under investigation.

#### 7.1.4 SERIOUS

An Unanticipated Problem or Protocol Deviation is serious if it meets the definition of a Serious Adverse Event or if it compromises the safety, welfare or rights of subjects or others.

#### 7.1.5 SERIOUS ADVERSE EVENT

An adverse event or suspected adverse reaction is considered serious if in the view of the investigator or the sponsor, it results in any of the following:

- Death,
- A life-threatening adverse drug experience
- Inpatient hospitalization or prolongation of existing hospitalization
- Persistent or significant incapacity or substantial disruption of the ability to conduct normal life functions
- A congenital anomaly/birth defect.
- Important medical events that may not result in death, be life-threatening, or require hospitalization may be considered a serious adverse drug experience when, based upon appropriate medical judgment, they may jeopardize the patient or subject and may require medical or surgical intervention to prevent one of the outcomes listed in this definition.

#### 7.1.6 DISABILITY

A substantial disruption of a person’s ability to conduct normal life functions.

#### 7.1.7 LIFE-THREATENING ADVERSE DRUG EXPERIENCE

Any adverse event or suspected adverse reaction that places the patient or subject, in the view of the investigator or sponsor, at immediate risk of death from the reaction as it occurred, i.e., it does not include a reaction that had it occurred in a more severe form, might have caused death.

#### 7.1.8 PROTOCOL DEVIATION (NIH DEFINITION)

Any change, divergence, or departure from the IRB-approved research protocol.

#### 7.1.9 NON-COMPLIANCE (NIH DEFINITION)

The failure to comply with applicable NIH Human Research Protections Program (HRPP) policies, IRB requirements, or regulatory requirements for the protection of human research subjects.

#### 7.1.10 UNANTICIPATED PROBLEM

Any incident, experience, or outcome that:

- Is unexpected in terms of nature, severity, or frequency in relation to
  - (a) the research risks that are described in the IRB-approved research protocol and informed consent document; Investigator's Brochure or other study documents, and
  - (b) the characteristics of the subject population being studied; **AND**
- Is related or possibly related to participation in the research; **AND**
- Suggests that the research places subjects or others at a *greater risk of harm* (including physical, psychological, economic, or social harm) than was previously known or recognized.

All treatment-limiting toxicities (see [Section 3.1.2](#)) that are possibly, probably, or definitely related to vandetanib and all serious adverse drug experiences (see [Section 7.1](#)), including oncology related events that meet the criteria for a serious adverse drug experience, whether related to vandetanib or not, will be reported to [name] by telephone within 24 hours of being made aware of the event:

[name].  
Pharmacology & Experimental Therapeutics Section  
Pediatric Oncology Branch  
National Cancer Institute  
[name]  
[name]  
[name]  
[contact]  
[contact]  
[contact]  
E-mail: [[contact]](mailto:[contact])

## 7.2 NCI-IRB AND CLINICAL DIRECTOR (CD) REPORTING

### 7.2.1 NCI-IRB AND NCI CD EXPEDITED REPORTING OF UNANTICIPATED PROBLEMS AND DEATHS

The Protocol PI will report in the NIH Problem Form to the NCI-IRB and NCI Clinical Director:

- All deaths, except deaths due to progressive disease
- All Protocol Deviations
- All Unanticipated Problems

- All non-compliance

Reports must be received within 7 days of PI awareness via iRIS.

#### 7.2.2 NCI-IRB REQUIREMENTS FOR PI REPORTING AT CONTINUING REVIEW

The protocol PI will report to the NCI-IRB:

1. A summary of all protocol deviations in a tabular format to include the date the deviation occurred, a brief description of the deviation and any corrective action.
2. A summary of any instances of non-compliance
3. A tabular summary of the following adverse events:
  - All Grade 2 **unexpected** events that are possibly, probably or definitely related to the research;
  - All Grade 3 and 4 events that are possibly, probably or definitely related to the research;
  - All Grade 5 events regardless of attribution;
  - All Serious Events regardless of attribution.

**NOTE:** Grade 1 events are not required to be reported.

#### 7.2.3 NCI-IRB REPORTING OF IND SAFETY REPORTS

Only IND Safety Reports that meet the definition of an unanticipated problem will need to be reported to the NCI IRB.

### 7.3 IND SPONSOR REPORTING CRITERIA

During the first 30 days after the subject receives investigational agent/intervention, the investigator must immediately report to the sponsor, using the mandatory MedWatch form 3500a or equivalent, any serious adverse event, whether or not considered drug related, including those listed in the protocol or investigator brochure and must include an assessment of whether there is a reasonable possibility that the drug caused the event. For serious adverse events that occur more than 30 days after the last administration of investigational agent/intervention, only report those that have an attribution of at least possibly related to the agent/intervention.

Required timing for reporting per the above guideline:

- Deaths (except death due to progressive disease) must be reported via email within 24 hours. A complete report must be submitted within one business day.
- Other serious adverse events as well as deaths due to progressive disease must be reported within one business day

Events will be submitted to the Center for Cancer Research (CCR) at: [[contact]](mailto:[contact]) and to the CCR PI and study coordinator.

#### 7.3.1 REPORTING PREGNANCY

##### 7.3.1.1 Maternal exposure

If a patient becomes pregnant during the course of the study, the study treatment should be discontinued immediately and the pregnancy reported to the Sponsor. The potential risk of

exposure of the fetus to the investigational agent(s) or chemotherapy agents (s) should be documented in box B5 of the MedWatch form “Describe Event or Problem”.

Pregnancy itself is not regarded as an SAE. However, as patients who become pregnant on study risk intrauterine exposure of the fetus to agents which may be teratogenic, the CCR is requesting that pregnancy should be reported in an expedited manner as **Grade 3 “Pregnancy, puerperium and perinatal conditions - Other (pregnancy)”** under the **Pregnancy, puerperium and perinatal conditions** SOC.

Congenital abnormalities or birth defects and spontaneous miscarriages should be reported and handled as SAEs. Elective abortions without complications should not be handled as AEs. The outcome of all pregnancies (spontaneous miscarriage, elective termination, ectopic pregnancy, normal birth, or congenital abnormality) should be followed up and documented.

If any pregnancy occurs in the course of the study, then the investigator should inform the Sponsor within 1 day, i.e., immediately, but **no later than 24 hours** of when he or she becomes aware of it.

The designated Sponsor representative will work with the investigator to ensure that all relevant information is provided to the Sponsor within 1 to 5 calendar days for SAEs and within 30 days for all other pregnancies.

The same timelines apply when outcome information is available.

#### 7.3.1.2 Paternal exposure

Male patients should refrain from fathering a child or donating sperm during the study and for 3 months after the last dose of Vandetanib.

Pregnancy of the patient’s partner is not considered to be an AE. However, the outcome of all pregnancies (spontaneous miscarriage, elective termination, ectopic pregnancy, normal birth, or congenital abnormality) occurring from the date of the first dose until 3 months after the last dose should, if possible, be followed up and documented.

## 7.4 SAFETY REPORTING CRITERIA TO THE PHARMACEUTICAL COLLABORATORS

All events listed below must be reported in the defined timelines to [contact].

The CCR Office of Regulatory Affairs will send all reports to the manufacturer as described below.

The study PI IND holder will notify AstraZeneca (SAE Fax line, [name]) in a **written** IND Safety Report (MedWatch, Form 3500A) of any adverse experience *associated* with the use of vandetanib that is both *serious* and *unexpected* at the time the MedWatch is reported to the FDA.

The study PI IND holder will also notify AstraZeneca **by telephone or by [contact])** of any *unexpected* fatal or life-threatening experience associated with the use of vandetanib as soon as possible but in no event later than 7 calendar days of initial receipt of the information (at the time the MedWatch is submitted to the FDA).

A Fax cover page should accompany any MedWatch form that is sent to AstraZeneca indicating the following:

- Vandetanib Investigator Sponsored Study (ISS)

- The investigator IND number assigned by the FDA
- The investigator's name and address
- The trial name/title and AstraZeneca reference number

The Investigative site must also indicate, either in the SAE report or the cover page, the causality of events in relation to all study medications and if the SAE is related to disease progression, as determined by the principal investigator.

Any event or hospitalization that is unequivocally due to progression of disease, as determined by the PI, will not be reported as an SAE, however should be communicated to AstraZeneca.

All SAEs have to be reported to AstraZeneca, whether or not considered causally related to the investigational product. All SAEs will be documented.

## **7.5 DATA AND SAFETY MONITORING PLAN**

Vandetanib has been approved by the US Food and Drug Administration (FDA) for treatment of advanced MTC and currently has a well-established toxicity profile. Therefore, only unexpected  $\geq$  grade 2 adverse events at least possibly related to study drug or any  $\geq$  grade 3 or adverse events observed in patients enrolled on the trial will be recorded by the Principal and Associate Investigators, and attribution of these events to vandetanib will be determined at the end of each treatment cycle in each subject.

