- **Hypertension (HTN):**

- **Pediatric Participants:**

For pediatric patients, the ULN for blood pressure is defined as a diastolic BP at the 95th percentile from age and gender-appropriate normal values (see [Appendix 2](#)). Pediatric patients with a diastolic blood pressure >95% for age and gender should have blood pressure measurement repeated x2 with an appropriate size cuff, and hypertension (HTN) is defined as at least 2 (of 3) measurements exceeding the ULN (See [Appendix 2](#) and [Appendix 3](#)). Treatment-limiting hypertension is defined as:

- A diastolic BP on at least 2 of 3 measurements that is more than 25 mm Hg above the ULN for age and gender.
- A diastolic BP on at least 2 of 3 measurements that is above the ULN but not more than 25 mm Hg above the ULN and that does not return to within the normal range after 14 days on single agent antihypertensive therapy.
- Grade  $\geq 4$  (CTCAE v.4) hypertension.

- **Adult Participants:**

[Appendix 4](#) will be used for the grading of vandetanib-associated hypertension in adults, for immediate and intermediate-term management, and for the determination of vandetanib modification. Hypertension in adult patients is defined as a systolic blood pressure > 150 mmHg or a diastolic pressure > 90 mm HG despite optimal medical management, for patients  $\geq 18$  years of age, and may include hypertension-related symptoms as reported by patient (e.g., headache), or other relevant changes associated with development of hypertension (e.g., ECG abnormalities) (See [Appendix 4](#) and [Appendix 5](#)).

Treatment-limiting hypertension is defined as:

- A diastolic BP on at least 2 of 3 measurements that is more than 90 mm Hg or systolic BP that is more than 150 mm Hg, that does not return to within the normal range after 14 days despite maximum medical therapy.
- Grade  $\geq 4$  (CTCAE v.4) hypertension.

- **QTc Prolongation:**

Any clinically significant abnormal findings or QTcB prolongations will be recorded as AEs.

Participants with QTc prolongation should have serum electrolytes (including potassium, calcium and magnesium) measured. If serum electrolytes are outside the normal range, the abnormality should be corrected before determining whether a patient has treatment-limiting QTc prolongation.

In addition to scheduled ECG, additional ECGs should also be performed in the event of QTcB prolongation, both during and post the prolongation period.

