## **6 DATA COLLECTION AND EVALUATION**

### **6.1 DATA COLLECTION**

The PI will be responsible for overseeing entry of data into an in-house password protected electronic system (C3D) and ensuring data accuracy, consistency and timeliness. The principal investigator, associate investigators/research nurses and/or a contracted data manager will assist with the data management efforts. All data obtained during the conduct of the protocol will be kept in secure network drives or in approved alternative sites that comply with NIH security standards. Primary and final analyzed data will have identifiers so that research data can be attributed to an individual human subject participant.

All adverse events, including clinically significant abnormal findings on laboratory evaluations, regardless of severity, will be followed until return to baseline or stabilization of event.

An abnormal laboratory value will be recorded in the database as an AE **only** if the laboratory abnormality is characterized by any of the following:

- Results in discontinuation from the study
- Is associated with clinical signs or symptoms
- Requires treatment or any other therapeutic intervention
- Is associated with death or another serious adverse event, including hospitalization.
- Is judged by the Investigator to be of significant clinical impact

- If any abnormal laboratory result is considered clinically significant, the investigator will provide details about the action taken with respect to the test drug and about the patient's outcome.

**End of study procedures:** Data will be stored according to HHS, FDA regulations, and NIH Intramural Records Retention Schedule as applicable.

**Loss or destruction of data:** Should we become aware that a major breach in our plan to protect subject confidentiality and trial data has occurred, the IRB will be notified.

Clinical data will be shared with AstraZeneca.

Questionnaire (PROMIS and Distress Thermometer) data will be entered into an SPSS (version 12.0.1), SPSS, Chicago, IL) database by a research assistant. Personal identifiers will not be used when collecting and storing data. Questionnaire data will be linked with clinical data through the use of the unique subject identification number. Files will be stored in password-protected folders and accessible only to the personnel in the POB NCI Psychosocial Support and Research Program.

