### **8.2 ANALYSIS OF SECONDARY ENDPOINTS**

#### *Safety and Tolerability*

Patients will be carefully monitored for adverse events; which will be recorded in a daily patient diary and documented by the care providers. These will be graded according to CTCAE version 4.0. Information regarding type of adverse event, grade, attribution, temporal occurrence and frequency will be summarized using descriptive methods.

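### Section 7.5 limits which adverse events are recorded and attributed, while section 8.2 promises a summary without that limit, so expected grade 2 events are not assured of reaching it

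*Combined protocol and SAP*

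**What the plan says.** Section 7.5 (Data and Safety Monitoring Plan) gives a reason for collecting less: vandetanib is already approved for another cancer and its toxicity is well characterized. It then restricts recording to unexpected events, at or above "grade 2 adverse events at least possibly related to study drug or any" events at or above "grade 3 or adverse events observed in patients enrolled on the trial will be recorded by the Principal and Associate Investigators". The wording after the second grade threshold is garbled. Attribution is tied to the same subset: "attribution of these events to vandetanib will be determined at the end of each treatment cycle in each subject".

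Section 8.2 (Safety and Tolerability) describes the analysis. Its source is toxicity information "which will be recorded in a daily patient diary and documented by the care providers. These will be graded according to CTCAE version 4.0". The summary itself is then promised in these terms: "Information regarding type of adverse event, grade, attribution, temporal occurrence and frequency will be summarized using descriptive methods". No limit by grade, relatedness or expectedness appears there.

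Two other sections bear on the question. Section 6.1 says that all adverse events, "regardless of severity, will be followed until return to baseline or stabilization of event". Its one restriction on database entry concerns laboratory findings: "An abnormal laboratory value will be recorded in the database as an AE" only if it meets one of the listed conditions. Section 3.1.2 adds, under QTc prolongation: "Any clinically significant abnormal findings or QTcB prolongations will be recorded as AEs".

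**The concern.** Safety and toxicity in this population is a secondary objective (1.1.2.1). Section 10.2 says that the drug has not been used before in wt-GIST and that its tolerability and toxicity are under study for that reason. The argument in 7.5 for recording less therefore sits badly with the trial's own aim.

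The events that 7.5 leaves out are likely to be the familiar ones. Section 10.4.1 names rash, diarrhea and asymptomatic QTc prolongation as the most common in adults. If such an event reaches grade 2, is related, and counts as expected, 7.5 does not require the investigators to record or attribute it, yet 8.2 needs both its grade and its attribution. A reader of the final safety table could not tell an event that did not occur from one that was not recorded.

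**Working it through.** No sample size, power or error rate is involved, so there is no figure in the plan to reproduce. The check follows one event through the document and then sets out what an omission would do to a reported rate.

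**1. The rules side by side.** Take a non-serious grade 2 diarrhea or rash, judged related and expected.

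- *7.5:* it is not unexpected and is below grade 3, so it falls outside the set to be recorded and attributed. Reading the garbled phrase as covering any adverse event would rescue it, but would leave the opening restriction with no effect.
- *8.2:* it is an adverse event to be graded, attributed and summarized.
- *6.1:* it is followed. That is not an instruction to enter, grade or attribute it. The limit on database entry for laboratory values suggests that clinical events have no limit, but the section does not say so.
- *3.1.2:* the rule concerns clinically significant findings or QTcB prolongations. It does not address diarrhea or rash.
- *Diary (Appendix 8):* it collects episode counts, stool consistency, a nausea rating and rash, with no field for CTCAE grade or attribution.
- *Clinic record:* 4.4 asks for CTCAE grading of rash and 4.5.2 sets rules by diarrhea grade, so a grade may exist in the notes.
- *3.1.1:* escalation after cycle 3 depends on related toxicities in cycles 1 to 3 being below grade 2, with stated exceptions. Expectedness plays no part. Grade and relatedness must therefore be judged for any patient considered for escalation, but the rule does not order that they be entered in the database.

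Sections 7.5 and 8.2 give different answers for the same event, and no section gives either precedence. Grade 1 events and unrelated grade 2 events are also outside 7.5.

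**2. Scale.** Section 8.3 reports nine patients enrolled before closure. Assume that all nine were treated.

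- One patient whose only occurrence of an event is omitted: 1/9 = 0.111, or 11.1 percentage points off that event's reported frequency.
- The any-grade rates in 11.1.6 (300 mg monotherapy, N = 1846) give ceilings: diarrhea 946/1846 = 0.5125, and 9 × 0.5125 = 4.6 patients; rash 672/1846 = 0.3640, and 9 × 0.3640 = 3.3 patients.
- The documents give no split by grade. If 10% to 50% of affected patients had grade 2 as their worst grade (an assumption), the expected number omitted would be 0.46 to 2.31 of nine for diarrhea (4.61 × 0.1 and 4.61 × 0.5) and 0.33 to 1.64 for rash (3.28 × 0.1 and 3.28 × 0.5).

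These counts are illustrations. Patients here start at 200 mg or 100 mg/m² (3.1.1), so the 300 mg rates may not carry over. Under 7.1.3 expectedness also depends on the listed severity, and 11.1.6 lists no grades.

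**The case against.** The best case for the plan is that 7.5 is a deliberate choice of selective safety collection for an approved drug, with its reason stated. On this reading 7.5 governs monitoring, while 6.1 and 8.2 govern data and analysis. Section 8.2 names its own sources, the diary is reviewed at each clinic visit (3.5.1.8), and the principal investigator reviews adverse event data for each patient (7.5.1). The escalation rule in 3.1.1 and the re-escalation rule in 3.3.2 also mean that some grade 2 events are graded at the time. The endpoint is descriptive and accrual is closed.

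Much of this stands. It shows that the information probably exists at source, at least for cycles 1 to 3, and it keeps the stakes modest. It does not remove the conflict: 7.5 speaks of recording, it alone says when and for which events attribution is determined, and 8.2 promises attribution without the same limit. The stated reason also does not answer 10.2 or the safety objective.

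Three stronger readings are tempting and are not supported.

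- A reader might infer that expected grade 2 events were lost. Appendix 10 (the reactions and symptoms log) and the case report forms are not in the supplied text, and they may collect these events.
- A reader might infer that the limit in 7.5 was copied by mistake from the similar IRB list in 7.2.2. The two resemble each other, but 7.5 gives its own reason.
- A reader might take 3.1.2 to require recording of QTcB prolongation at every grade. It does not mention grade, and its condition of clinical significance may apply to both items it names.

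**Conclusion.** The conflict between 7.5 and 8.2 is real and should be corrected. If 7.5 is followed as written, the safety summary would understate expected grade 2 toxicity, by 11.1 percentage points for each patient omitted from an event's count, assuming that all nine were treated. Sections 3.1.2 and 6.1 close only part of the gap.

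Confidence is high for the conflict in the text and low for the size of any actual loss, which depends on unseen data collection forms, on an unknown share of grade 2 events, and on which of them count as expected.

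**What to change.** Reconcile 7.5 with 8.2, 6.1 and 3.1.2.

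- In 7.5, make the recording rule cover all events of grade 2 or higher that are at least possibly related to vandetanib, expected or not, and all events of grade 3 or higher, each with CTCAE grade and attribution. Correct the garbled phrase. Keep the rules in 3.1.2 and 6.1 as stated additions.
- Leave the IRB reporting threshold in 7.2.2 unchanged.
- State in 8.2 and in the safety table which events were systematically captured, by grade and by relatedness. Grade 1 and unrelated grade 2 events would still fall outside 7.5 and must not be read as absent.
- For the nine patients, check the database first. If expected related grade 2 events are there with grade and attribution, only the text needs to change. If not, enter them from existing clinic notes (including the cycle 1 to 3 escalation assessments), diaries and logs, and flag any graded retrospectively.

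The cost is a wording change and, at most, modest data entry for nine patients. Grade and attribution will be less certain for events graded retrospectively. No dose or other clinical rule changes.
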